or video-recorded sermons. We anticipate that families will have up 30 activities to choose from with the average activity length to be 10 minutes. The toolbox will be placed online. Participants will be able to access the toolbox via a tablet computer that will be provided to them. Before testing, member checks will occur with the design team and stakeholders for their feedback on fittingness and readiness for testing of Faith-HAT.

Aim 2. Test the feasibility and explore preliminary effectiveness of employing Faith-HAT. We will achieve this aim by conducting a feasibility clinical trial ($n = 30$). Our feasibility outcomes will include success in recruitment, engagement, and retention. Our effectiveness outcomes will include caregiver-reported perceived change in behavioral problems in PLWD as the primary outcome and caregivers' self-reported perceived psychological well-being (e.g., stress, burden, depression) and objectively measured physiological stress response (e.g., heart rate variability, skin conductance) as the secondary outcomes. We will use quantitative surveys, qualitative interview data, and caregiver diaries to assess psychological well-being and a wearable wristband to assess the physiological wellbeing.

Figure 3. Implementation Matrix

1-Design: A single arm pre-post design will be employed. Participants will be asked to take part in in-person survey and physiological baseline data collection, engage weekly in at least 3 activities from the Faith-HAT with person caring for living with ADRD for **6 weeks**, complete 12 weekly diary entries online through RedCap platform, and provide in-person survey and physiological endline data **immediately post-intervention and at 6-weeks post-intervention**. In addition to qualitative and quantitative measures, tracking of the enrollment and attrition rate will enable us to compute the “feasibility” of the program. Within the framework of a feasibility study,⁷³⁻⁷⁵ 12 weeks is a reasonable amount of time for the behavior toward the use of the Faith-HAT to be adopted and show meaningful effects.

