4- Intervention: The caregiver/PLWD dyad will engage in Faith-HAT for **6 weeks**. They will select activities from Faith-HAT at least 3 times a week. Possible examples of these activities include devotional readings, prayer, music, religious images, and video and audio recorded sermons. Results from Aim 1 will further specify delivery characteristics for Faith-HAT. Faith-HAT will be placed on online, which requires little technical know-how by users. The PI will provide training to participants on how to use the Faith-HAT and online diary on the tablet computer provided by the project. Training and implementation will be monitored with a checklist documenting the participant's ability to use the device, access the toolbox through Brightspace, implement the intervention, and understand the feedback in relation to troubleshooting. The "dose" and frequency of use of the interventions will be calculated by determining the number of days/weeks the intervention was used for **6 weeks**. The quality of delivery of Faith-HAT will be assessed during weekly online diary checks.

5- Study visits: Enrollment, Baseline, and Endline: Once eligible, the PI will schedule a visit with the participating caregiver to consent and enroll, provide training and instruction on Faith-HAT, and obtain baseline data. Baseline caregiver-reported behavioral problems in PLWD; caregivers' self-reported psychological well-being (stress, burden, depression); and objective physiological measures of stress response (heart rate variability, skin conductance) will be collected. Each week for **6 weeks** the dyad will be asked to complete at least 3 activities from the Faith-HAT, and the caregiver will complete 12 weekly diary entries online. At the end of the intervention, the PI will schedule a visit and participants will provide survey and physiological endline data **immediately post-intervention and at 6-weeks post-intervention.** **Figure 3** shows the various measures collected at each visit.

6. Study procedures: **Figure 3** illustrates the project's associated procedures and analytic plan.

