(a) Quantitative Analysis: Quantitative data will be entered at the time of each interview directly into the dedicated project tablet computer and saved on Emory's secure REDCAP platform. All data entry screens are set up in REDCAP and, where possible, include data delimiters (i.e., skip patterns, valid range limits) to ensure correctness and minimize missing data. Data will be exported into SPSS monthly and syntax run for cleaning, further data verification and file concatenation. Descriptive statistics will be computed through SPSS v 24 to examine patient characteristics. Sex as a biological factor will also be considered as a variable for analysis. While the primary expected products of this work pertain to feasibility, and our study is not powered to conduct formal hypothesis testing, we will perform preliminary analyses with a multilevel modeling framework to assess relative group changes in scores for measures of stress, burden, and behavioral problems of PLWD. Although effect sizes will not be estimated,⁸⁹ general linear mixed models will be applied to account for the repeated measurements for each study participant and a group by time term will be included in the model to gauge trends and direction of effects. In preliminary analyses, descriptive statistics and frequency distributions will be examined to identify outliers and ensure integrity of merged files. For all multi-item scales, internal consistency will be examined using Cronbach's alpha and associated statistics (e.g., item-total correlations, alpha if item deleted). Formal test-retest/inter-rater reliability coefficients will be computed as data are concatenated.

(b) Qualitative Analysis: All interviews will be conducted by the PI, audio-recorded, and transcribed verbatim. To reduce bias, field notes and journaling will be maintained during this phase. Interviews and diary entry data

will be managed in NVivo 12 software. Data collection and analysis will be performed concurrently. Qualitative content analysis will examine manifest and latent content of the diary entry data.⁹⁰ The PI will work with another member of the research team to independently review transcripts and identify codes and the research team will be brought in to resolve any discrepancies among the independently developed codes. Member check will occur to serve as validation of the interpretation.

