Aim 3. Construct a refined toolbox of meaningful faith-based home activities. No recruitment of participants and active data collection will occur for this aim. Qualitative and quantitative results from all data collection points from Aim 2 will be matched and compared to assist in refining the design of the Faith-HAT. The integration and interpretation of results through joint display and narrative discussion will be shared with the design team. Details of narrative discussion including caregiver discussion of activities to add, other ways to use the Faith-HAT, and circumstances under which engagement in Faith-HAT with the family member were optimal will be reviewed by the research and design team to develop a plan for program revision. Reasons for participant withdrawal and participant feedback on delivery characteristics will also be used to determine what components of the Faith-HAT will need to be revised. The research and design team will work together to produce a refined Faith-HAT program. Member checks of the refined toolbox with participants in Aims 1 and 2 will be conducted to improve the authenticity of the work and improve the accuracy, validity, and transferability of design readiness for deployment for a fully powered clinical trial.

Informed Consent Process:

Interested stakeholders and caregivers will be contacted by the PI or member of the research team to schedule a time to consent prior to data collection. Consents will be obtained at mutually agreed locations or via videoconference platform. Participants will be given the option to provide verbal consent after a discussion using a videoconference platform. After the videoconference discussion and verbatim review of verbal consent document, verbal informed consent will be obtained from the participant or legal representative and a copy of the consent will be mailed to them for their records.

Consents will be obtained at mutually agreed locations or provided by phone/videoconference. Consents will be obtained prior to data collection and the primary investigator will be responsible for obtaining consent.

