Phase 1 participants will receive \$25 honorarium upon completion of their semi-structured interview. Phase 2 caregiver participants will receive a \$25 honorarium for each baseline, endline, and qualitative interview completed for a total of \$75. In addition, they will also receive \$5 for each weekly diary entry completion, for an additional honorarium of \$60. Caregiver participants in Phase 2 possible compensation for total study participation is \$135.

Limitations, Challenges, and Strategies: This clinical trial feasibility study is an early stage of intervention development. A limitation of this study is related to not incorporating a control group into the design to avoid bias. Therefore, causal inferences regarding effects will not be made from the results of implementing the Faith-HAT. Accuracy of family caregiver report of behavior changes of the PLWD might be questionable due to recall bias. To counterbalance this challenge, caregiver participants will complete weekly entries about behavioral occurrences by their family member in their caregiver diaries. Asking participants to complete diaries of their weekly experiences allows for the gathering of their perceptions, thoughts, and feelings, as well as their family member's behavior and caregiving in context. However, using weekly caregiver diaries for data collection presents a challenge of maintaining caregiver motivation to ensure the diary entries are completed. Members of the research team will send weekly text message reminders, establish good working relationships with participants, and provide positive reinforcements to maintain motivation throughout study period. Recruiting AA participants into clinical research has been an ongoing challenge. If the aforementioned recruitment strategies do not obtain the desired sample, recruitment will be extended to advertising through social media, radio, senior centers, community newsletters, and other public venues.

Bibliography and References Cited

1. Pew Research Center. (2015). America's changing religious landscape. Retrieved from: <http://www.pewforum.org/2015/05/12/americas-changing-religious-landscape/>
2. Pew Research Center. (2014). U.S. public becoming less religious. Numbers, Facts, and Trends Shaping the World. <http://www.pewforum.org/2015/11/03/u-s-public-becoming-less-religious/>

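### Aim 2 has a single arm, so the group-by-time term named to show direction of effects is not the pre-post change under either reading of group

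*Combined protocol and SAP*

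**What the plan says.** Item 7(a) under Aim 2 describes a multilevel framework "to assess relative group changes in scores for measures of stress, burden, and behavioral problems of PLWD". It then specifies general linear mixed models for the repeated measurements, in which "a group by time term will be included in the model to gauge trends and direction of effects". No other term or contrast is given the task of showing direction. The same paragraph lists sex as a variable to be considered, without linking it to this term. It also says that effect sizes will not be estimated and that the study is not powered for formal tests.

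The design is stated in item 1-Design: "A single arm pre-post design will be employed". The Limitations section agrees: "A limitation of this study is related to not incorporating a control group into the design to avoid bias". The opening of Aim 2 names "caregiver-reported perceived change in behavioral problems in PLWD as the primary outcome". Under Aim 3, the Aim 2 results "will be matched and compared to assist in refining the design of the Faith-HAT".

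Figure 3 is not visible in the text available for review. Item 5 says that it "shows the various measures collected at each visit", and item 6 says that it sets out the project's "associated procedures and analytic plan".

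**The concern.** A group-by-time term answers a question about two or more groups: did they change by different amounts? Aim 2 asks a one-sample question: did scores change from baseline? The plan names the first kind of term to answer the second kind of question, in a study with nobody in a second arm.

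At stake is the exploratory effectiveness readout for stress, burden and behavioral problems. An analyst who follows 7(a) literally would look for direction in a coefficient that either has no value of its own or describes a subgroup contrast. In the second case, a uniform improvement across subgroups would read as no effect.

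**Working it through.** **Inputs.** Arms G = 1 (item 1-Design). Sample n = 30 dyads (item 2, Participants). Visits T = 2 according to Aim 2 in section (B), or T = 3 according to items 1-Design and 5. The documents give no SD, effect size or dropout rate, and 30 comes from a rule of thumb, so the plan has no figure of its own to reproduce here.

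**Step 1: group read as arm.** The interaction has (G − 1)(T − 1) degrees of freedom.
- T = 2: (1 − 1)(2 − 1) = 0
- T = 3: (1 − 1)(3 − 1) = 0

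The fixed-effects matrix with intercept, group, time and group × time has 2T columns. For 30 participants it has 4 columns and rank 2 when T = 2, and 6 columns and rank 3 when T = 3. Intercept and time alone already have ranks 2 and 3, so the group columns add nothing.

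**Step 2: what can still be estimated.** Let every participant carry the same group code g. The expected change from baseline to a later visit is β(time) + g·β(group × time). The data identify this sum, Δ, but not its parts. With g = 1, the pairs (Δ, 0), (Δ/2, Δ/2) and (0, Δ) fit equally well, so the interaction coefficient can be 0%, 50% or 100% of the change. In one simulated two-visit data set with mean change −0.589, three ways of resolving the redundancy gave interaction coefficients of 0, −0.294 and −0.589. The residual sum of squares was 56.494 each time, and so was the visit change of −0.589.

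**Step 3: group read as a subgroup, for example sex.** The term now has T − 1 = 1 or 2 degrees of freedom, but it equals (change in one sex) − (change in the other). If both change by −0.5, it is −0.5 − (−0.5) = 0. A large simulation of that case gave 0.003 for sex × time and −0.506 for time. The contrast is also imprecise. At n = 30 its 95% half-width is 0.75 SD of change for an assumed 15/15 split and 0.93 for an assumed 6/24 split.

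**Step 4: precision of the visit change.** Half-width = t(0.975, 29)/√30 = 2.045/5.477 = 0.373 SD of the individual change, with complete pairs. With 24 pairs (an assumed 20% loss) it is 2.069/4.899 = 0.422.

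**Step 5: covariance for the replacement model.** A random intercept alone forces equal correlation between all visits. Suppose instead three equally spaced visits with correlation ρ between neighbours and ρ² between first and last. The random-intercept model in effect uses the average, (2ρ + ρ²)/3. The ratio of its variance to the true variance is then:
- baseline to last visit: (3 + ρ)/[3(1 + ρ)], which is 0.778 at ρ = 0.5 and 0.704 at ρ = 0.8
- baseline to middle visit: (3 + ρ)/3, which is 1.167 and 1.267

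Multiplying the nominal half-width of 0.365 (58 degrees of freedom) by the square roots gives 0.32 and 0.31 SD for the later change, which is too narrow, and 0.39 and 0.41 for the earlier one, which is too wide. In simulation over the assumed range ρ = 0.5 to 0.8, coverage was 90–92% for the later change and about 97% for the earlier one, against 95% for paired intervals at each visit.

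**Step 6: levels of time.** Weeks are counted from the start of a 6-week intervention.

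| Place | Weeks |
|---|---|
| (B) Aims, Aim 2 | 0, 12 |
| Items 1-Design and 5 | 0, 6, 12 |
| Item 6(c), wristband | 0, 6 |

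These differ, but Step 1 gives 0 for both T = 2 and T = 3, so the schedule does not cause the redundancy.

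**The case against.** Several points on the other side have force.

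- *Group is undefined, so 0 degrees of freedom is conditional.* This stands. A subgroup reading gives T − 1 degrees of freedom, and Figure 3 might define subgroups. But no figure can make an arm-by-time term estimable with one arm, and Step 3 shows that a subgroup term is still not the pre-post change.
- *The model may also carry a time effect.* This stands too. The text does not exclude one, and the visit change is the same however the redundancy is handled. A reader might infer that the planned model cannot deliver a pre-post change, or that the software would fail. The documents support neither inference. The fault is that the plan points to the wrong term.
- *The analysis is exploratory.* Correct: formal testing and causal inference are both disclaimed. A reader might infer that toolbox refinement depends on this coefficient. Aim 3 does not say so; it also draws on narrative discussion, reasons for withdrawal and participant feedback.
- *The plan declines to estimate effect sizes, so reporting a change contradicts it.* The clause needs clarifying. The reference attached to it concerns, by its title, pilot studies and power calculations, which suggests standardized effects for powering a later trial. Direction cannot be read without a signed change, and a raw mean change with its CI can serve that descriptive purpose.
- *Timing is a separate matter.* Largely so. The model in 7(a) does not name the wristband measures, and the week numbers rest on a 6-week intervention. The schedule matters here only because it sets the levels of visit.

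**Conclusion.** The point holds as a wording error in the exploratory analysis and should be fixed. If group means arm, the term has 0 degrees of freedom with two or three visits. If it means a subgroup, it is a difference in change between subgroups. Neither is the overall change from baseline. That this change is the intended target is an inference, resting on the primary effectiveness outcome and the single-arm pre-post design.

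The size of the problem is modest. The change remains estimable, with a 95% half-width of about 0.37 SD of individual change if all 30 pairs are complete. That figure describes what the study can deliver, not damage done by the error. A reader might go further and conclude that the feasibility outcomes or the sample size of 30 are compromised. They are not, since neither depends on this model.

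**What to change.** In 7(a), replace the wording on changes between groups and the group-by-time term with:

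*A linear mixed model with categorical visit as the fixed effect and unstructured within-participant covariance (or, equivalently for complete data, a paired analysis at each post-baseline visit) will be fitted. Direction will be read from the mean raw change from baseline at each post-baseline visit, reported descriptively with its 95% CI. Any sex-by-visit term will be in a separate descriptive model.*

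In the same edit, state that the clause on effect sizes refers to standardized effect sizes for powering a later trial and not to the raw mean change. A random intercept alone is not recommended, for the reason in Step 5.

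As a secondary step, reconcile the assessment times in (B) Aims, items 1-Design, 5 and 6(c), and Figure 3, so that visit has one agreed set of levels.

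The cost is a few sentences and one consistent schedule. No new participants or measures are needed.
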